9.4.1.3. Maintenance Study (Phase 3 Maintenance Study)

The primary, major secondary, and other endpoints evaluate the efficacy of guselkumab versus placebo, in participants with moderately to severely active UC who were in clinical response after 12 weeks of IV guselkumab induction therapy.

Primary Endpoint

The primary endpoint in this study is clinical remission at Week M-44 (Maintenance Week 44).

Major Secondary Endpoints

- Symptomatic remission at Week M-44.
- Endoscopic healing at Week M-44.
- Corticosteroid-free (ie, not requiring any treatment with corticosteroids for at least 8 weeks prior) clinical remission at Week M-44.
- Clinical response at Week M-44.
- Histologic-endoscopic mucosal healing at Week M-44.
- IBDQ remission at Week M-44.
- Fatigue response at Week M-44.
- Clinical remission at Week M-44 among the participants who had achieved clinical remission at maintenance baseline (ie, maintenance of clinical remission at M-44).
- Endoscopic normalization at Week M-44.

Note: The final ordering of the major secondary endpoints will be provided in the SAP for this study.

Other Endpoints

Clinical Endpoints

- Clinical remission at Week M-44, based on a stool frequency subscore of 0, a rectal bleeding subscore of 0, and an endoscopy subscore of 0 or 1 with no friability present on endoscopy.
- Endpoints based on other definitions of clinical response and clinical remission at Week M-44 (to be specified in the SAP).
- Change from maintenance baseline in the modified Mayo score at Week M-44.
- Change from maintenance baseline in the partial Mayo score at each visit through Week M-44.
- Change from maintenance baseline in the stool frequency and rectal bleeding subscores at each visit through Week M-44.
- Rectal bleeding subscore of 0 at each visit through Week M-44.
- Stool frequency subscore of 0 or 1 at each visit through Week M-44.

-
- Change from maintenance baseline in the full Mayo score at Week M-44.
 - Symptomatic remission at each visit through Week M-44.
 - Durable symptomatic remission through Week M-44 (symptomatic remission for $\geq 80\%$ of all visits between Week M-0 and Week M-44 [ie, at least 10 of 12 visits], which must include Week M-44).
 - Symptomatic remission at each visit through Week M-44 among the participants who had achieved symptomatic remission at maintenance baseline.
 - Endoscopic healing at Week M-44 among the participants who had achieved endoscopic healing at maintenance baseline.
 - Clinical remission at Week M-44 and not receiving corticosteroids for at least 12 weeks prior to Week M-44.
 - Clinical remission at Week M-44 and not receiving corticosteroids for at least 4 weeks prior to Week M-44.
 - Clinical response and not receiving corticosteroids at Week M-44.
 - Change from maintenance baseline in the average daily prednisone-equivalent corticosteroid dose (excluding budesonide and beclomethasone dipropionate) at each visit through Week M-44 among the participants who were receiving concomitant corticosteroids at maintenance baseline.
 - Elimination of concomitant corticosteroids at Week M-44 among the participants who were receiving concomitant corticosteroids at maintenance baseline.
 - Elimination of corticosteroids for at least 12 weeks prior to Week M-44 among participants who were receiving corticosteroids at maintenance baseline.
 - Elimination of corticosteroids for at least 4 weeks prior to Week M-44 among participants who were receiving corticosteroids at maintenance baseline.
 - Clinical response, clinical remission, endoscopic healing, endoscopic normalization, histologic-endoscopic mucosal healing, histologic-endoscopic mucosal healing (Alternative definition), and deep histologic-endoscopic mucosal healing at Week M-44 based on the local endoscopy subscores.
 - Primary and major secondary endpoints, histologic healing, histologic remission, histologic-endoscopic mucosal healing (alternative definition), and deep histologic endoscopic mucosal healing at Week M-44 by ADT-Failure status and biologic-failure status (eg, biologic-naïve, biologic-failure, biologic non-failure, and biologic-experienced without documented failure [ie, discontinued biologic therapy for other reasons], to be defined in the SAP), and by the colonic molecular prediction signature status at baseline.
 - Association of histologic-endoscopic mucosal healing, histologic improvement alone, or endoscopic improvement alone at Week M-0 with other efficacy parameters at Week M-44.
 - Change from maintenance baseline in UCEIS score at Week M-44.
 - UCEIS score ≤ 4 at Week M-44.
 - Histologic healing at Week M-44.

- Histologic remission at Week M-44.
- Histologic-endoscopic mucosal healing (Alternative definition) at Week M-44.
- Deep histologic-endoscopic mucosal healing at Week M-44.
- Other histologic endpoints based on other definitions using the Robarts Histopathology Index ([Mosli 2017](#)) and the Nancy Histological Index ([Marchal-Bressenot 2017](#)) at Week M-44 (to be specified in the SAP).
- Extraintestinal manifestations over time through Week M-44.

CRP and Fecal Calprotectin

- Change from maintenance baseline in CRP over time through Week M-44.
- Change from maintenance baseline in CRP over time through Week M-44 among participants with abnormal CRP at induction baseline.
- Change from maintenance baseline in fecal calprotectin over time through Week M-44.
- Change from maintenance baseline in fecal calprotectin over time through Week M-44 among participants with abnormal fecal calprotectin at induction baseline.
- Normalization of CRP over time through Week M-44 among participants with abnormal CRP at induction baseline.
- Normalization of fecal calprotectin over time through Week M-44 among participants with abnormal fecal calprotectin at induction baseline.

Patient-Reported Outcomes

- Change from maintenance baseline in the total IBDQ score and in each of the 4 IBDQ dimensions through Week M-44.
- A ≥ 16 or >20 -point improvement from induction baseline in the IBDQ total score at Week M-44.
- Maintenance of ≥ 16 or >20 -point improvement in IBDQ through Week M-44 among participants with a ≥ 16 or >20 -point improvement in IBDQ at the maintenance baseline compared with the induction baseline.
- IBDQ remission through Week M-44.
- Change from maintenance baseline in the domains T-scores of the PROMIS-29 and the pain intensity through Week M-44.
- Clinically meaningful improvement (to be defined in the SAP) in the domains T-scores of PROMIS-29 and the pain intensity through Week M-44.
- Fatigue response of PROMIS Fatigue Short Form 7a through Week M-44.
- Changes from maintenance baseline in the health state VAS score and EQ-5D dimensions through Week M-44.
- Change in PGIS from maintenance baseline at Week M-44.

- Abdominal pain (assessed by IBDQ question 13) and bowel urgency (assessed by IBDQ questions 16 and 24) at Week M-44 (to be defined in the SAP).

Health Economics

- UC-related emergency department visits, hospitalizations, and surgeries through Week M-44.
- Change from maintenance baseline in WPAI-GH through Week M-44.

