5. STATISTICAL ANALYSES

5.1. General Considerations

Descriptive statistics (i.e., N, mean, median, standard deviation (SD), interquartile (IQ) range, minimum, and maximum) will be used to summarize continuous variables. Counts and percentages will be used to summarize categorical variables. Graphical data displays (e.g., line plots) may also be used to summarize the data.

Analyses suitable for categorical data (e.g., chi-square tests, Cochran-Mantel-Haenszel tests, or logistic regression, as appropriate) will be used to compare the proportions of participants achieving selected endpoints (e.g., clinical response). In cases of rare events, Fisher's exact test will be used for treatment comparisons. Continuous response parameters measured at more than one postbaseline visit will be compared using Mixed-Effect Model Repeated Measure (MMRM) model (unless otherwise specified). If the normality assumption is in question, an appropriate transformation may be implemented before fitting MMRM model. Continuous response parameters measured at only one post-baseline visit will be compared using a stratified log-rank test or a log-rank test. The association between 2 categorical variables will be assessed based on a chi-square test and the association between a categorical variable and a continuous variable will be assessed based on a t-test.

A multiplicity-controlled testing procedure to control the Type-I error at a 2-sided 0.05 significance level over the primary and major secondary endpoints will be used (see Section 5.4.1.3.).

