5.4.1.1. Definition of Endpoints

The following endpoints are defined based on the corresponding scales; certain ICEs will be incorporated in the variable definition of each estimand as appropriate:

Clinical response: A decrease from induction baseline in the modified Mayo score (Section 5.3.1.1) by $\ge 30\%$ and ≥ 2 points, with either a ≥ 1 -point decrease from baseline in the rectal bleeding subscore or a rectal bleeding subscore of 0 or 1.

Symptomatic remission: a stool frequency subscore of 0 or 1 and a rectal bleeding subscore of 0, where the stool frequency subscore has not increased from induction baseline.

Histologic healing: neutrophil infiltration in < 5% of crypts, no crypt destruction, and no erosions, ulcerations or granulation tissue according to the Geboes grading system³ (i.e., Geboes score ≤ 3.1). (See Attachment 3).

Endoscopic healing: an endoscopy subscore of 0 or 1 with no friability present on the endoscopy.

Endoscopic normalization: An endoscopy subscore of 0 (which requires that no friability is present).

Histologic-endoscopic mucosal healing: achieving a combination of histologic healing and endoscopic healing with no friability present on the endoscopy.

IBDQ remission: total IBDQ score ≥ 170 (Irvine et al, 1994¹³; Higgins et al, 2005¹⁴).

Fatigue response: $a \ge 7$ -point improvement from induction baseline in PROMIS-Fatigue short form 7a.

Corticosteroid-free Clinical remission: not requiring any treatment with corticosteroids for at least 8 weeks prior to Week M-44 and also meeting the criteria for clinical remission at Week M-44.

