- Change from maintenance baseline in the full Mayo score at Week M-44.
- Change from induction baseline in absolute stool number at each visit through Week M-44.

- Statistical Analysis Plan CNTO1959UCO3001 Amendment 2
- Change from maintenance baseline in absolute stool number at each visit through Week M-44.
- Absolute stool number ≤ 3 at each visit through Week M-44.
- Rectal bleeding subscore of 0 at each visit through Week M-44.
- Stool frequency subscore of 0 or 1 at each visit through Week M-44.
- Change from induction baseline in the endoscopy subscore at Week M-0 and Week M-44.
- Change from maintenance baseline in the endoscopy subscore at Week M-44.
- Ulcerative Colitis Endoscopic Index of Severity (UCEIS) score ≤ 4 at Week M-44.
- Change from induction baseline in the UCEIS score at Week M-44.
- Change from maintenance baseline in UCEIS score at Week M-44.
- Extraintestinal manifestations over time through Week M-44 (i.e., arthritis/arthralgia, aphthous stomatitis, erythema nodosum, iritis/uveitis, pyoderma gangrenosum, and primary sclerosing cholangitis). The attributes and strategies for the ICEs will not be used for this endpoint. Analyses will include the following:
 - Presence of extraintestinal manifestations at maintenance baseline and Week M-44
 - Change from induction and maintenance baseline in arthritis/arthralgia pain level at Week M-44
 - Absence of extraintestinal manifestations among participants with extraintestinal manifestations at induction baseline and maintenance baseline
- Association of histologic-endoscopic mucosal healing, histologic healing, or endoscopic healing at Week M-0 with the following efficacy parameters at Week M-44 will be presented:
 - Clinical remission
 - Corticosteroid-free clinical remission
 - Symptomatic remission
 - IBDQ remission
 - Fatigue response
 - Mayo score
 - Partial mayo score
 - Modified mayo score
 - Stool frequency subscore
 - Rectal bleeding subscore
 - CRP and
 - Fecal calprotectin
 - Clinical flare

- Statistical Analysis Plan CNTO1959UCO3001 Amendment 2
- Clinical remission at Week M-44 and not receiving corticosteroids for at least 12 weeks prior to Week M-44.
- Clinical remission at Week M-44 and not receiving corticosteroids for at least 4 weeks prior to Week M-44.
- Clinical remission at Week M-44 and not receiving corticosteroids for at least 8 weeks prior to Week M-44 among the participants who were receiving concomitant corticosteroids at maintenance baseline.

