6.2. Appendix 2 Changes to Protocol-Planned Analyses

There were no changes to protocol-planned analyses, however, a few additional analyses which are not stated in the protocol are added in Section 5.5.

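### The protocol plans M-0 association analyses for histologic or endoscopic improvement alone, but the SAP substitutes overlapping healing groups that all contain the doubly healed participants and does not record the change

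*Protocol*

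**What the plan says.** Protocol section 9.4.1.3 plans, among the other clinical endpoints of the Maintenance Study: "Association of histologic-endoscopic mucosal healing, histologic improvement alone, or endoscopic improvement alone at Week M-0 with other efficacy parameters at Week M-44". It defines neither *improvement* nor *alone*. Section 9.4.1 leaves the analysis details to the SAP.

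SAP section 5.5 gives its version: "Association of histologic-endoscopic mucosal healing, histologic healing, or endoscopic healing at Week M-0 with the following efficacy parameters at Week M-44 will be presented". It then lists 13 M-44 parameters, from clinical remission to clinical flare.

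SAP section 5.4.1.1 supplies the definitions:
- Endoscopic healing is "an endoscopy subscore of 0 or 1 with no friability present on the endoscopy", with no condition on histology.
- Histologic healing requires few crypts with neutrophils, "no crypt destruction, and no erosions, ulcerations or granulation tissue according to the Geboes grading system", with no condition on endoscopy.
- The combined endpoint is "achieving a combination of histologic healing and endoscopic healing with no friability present on the endoscopy".

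The test is set in SAP section 5.1: "The association between 2 categorical variables will be assessed based on a chi-square test", and a t-test when one variable is continuous. SAP section 5.5.3 applies no multiplicity adjustment and reports nominal p-values. On departures from the protocol, SAP Appendix 2 states: "There were no changes to protocol-planned analyses", apart from added analyses in section 5.5.

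**The concern.** A list that sets the combined state beside each component *alone* reads most naturally as three separate groups: both healed, histology only, endoscopy only. The SAP list is not that. Its combined group is a subset of its other two groups, so the doubly healed participants enter all three analyses on the favourable side. Nothing in SAP sections 5.5, 5.5.1 or 5.5.3 makes the groups exclusive or adjusts one component for the other.

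At stake is how the results will be read. If double healing is what goes with a good M-44 outcome, histologic healing and endoscopic healing will each tend to show an association through their shared members. A reader who has the protocol's wording in mind could then credit a single component with predictive value that it lacks without the other. With 13 parameters and two component factors, 26 reported associations are open to this.

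**Working it through.** **Reproduction.** The documents give no figure for this analysis. The sample size and remission rates borrowed below do reproduce: 25% vs 45% gives 96.7% power with 161 per arm (SAP Table 3 states 97%) and 90.1% with 118 per arm (SAP Table 1 states 90%).

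**Overlap.** Let B be the share with both components healed at M-0, H histologic only, E endoscopic only, and N0 neither. The SAP's histologic factor compares B+H with E+N0. Its endoscopic factor compares B+E with H+N0. The reading of *alone* as without the other component needs H vs N0 and E vs N0. The SAP specifies neither contrast.

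**Formula.** Suppose a single component adds nothing, so that H, E and N0 share one M-44 remission rate p0, and B has rate pB. The marginal difference is then

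d = [share of B within the component-healed group] × (pB − p0),

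which is above zero whenever pB > p0. The test statistic is z = d / √[p̄(1−p̄)(1/n1 + 1/n2)], and the chance of p<0.05 is about Φ(z − 1.96).

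**Illustration 1, all shares and rates assumed:** pB = 50%, p0 = 28%.

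| Factor | B | Only | Healed vs not | d (points) | z, N=484 | Chance | z, n=161 | Chance |
|---|---|---|---|---|---|---|---|---|
| Histologic | 25% | 15% | 41.8% vs 28% | 0.25/0.40 × 22 = 13.8 | 3.14 | 88% | 1.81 | 44% |
| Endoscopic | 25% | 10% | 43.7% vs 28% | 0.25/0.35 × 22 = 15.7 | 3.49 | 94% | 2.01 | 52% |
| Histologic, second mix | 15% | 20% | 37.4% vs 28% | 0.15/0.35 × 22 = 9.4 | 2.13 | 57% | 1.23 | 23% |

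**Illustration 2, tied more closely to the protocol.** Section 9.2.2 assumes, at I-12 on guselkumab, 60% clinical response, 27% endoscopic healing and 17% combined healing. Suppose that all healed participants are responders and that these rates carry over to the randomized maintenance population. Then B = 17/60 = 28.3%, endoscopic healing = 27/60 = 45%, and E = 16.7%. The documents do not give H, so it is varied from 5% to 25%. The overall M-44 rate is (25 + 45 + 45)/3 = 38.3%. With p0 assumed at 30% or 33.3%, matching that overall rate requires pB = 59.4% or 51.1%.

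In 20,000 simulated trials per scenario, with no single-component effect:
- The SAP grouping, pooled N = 484, is significant in 56% to over 99% of trials (histologic) and in 70% to 99% (endoscopic).
- In one arm of 161 (p0 = 30%, H from 5% to 20%), it is significant in 61% to 86% and in 67% to 68%.
- The exclusive contrasts, H vs N0 and E vs N0, reject in 4.6% to 5.3%, which is nominal.

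**The case against.** The best reply is that *alone* may mean taken as a single criterion rather than as the composite. On that reading the SAP matches the protocol. The protocol leaves *improvement* undefined and defers the details, so the SAP had to choose terms, and it chose defined ones. This has some force, but neither document says which reading is meant, and next to a combined category the more natural one is without the other component. Either way the wording needs settling.

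Other parts of the reply stand and limit the point:
- A reader might infer that the SAP would report associations that do not exist. It would not. In the first row above, 41.8% vs 28% is a real marginal difference, and the chi-square test detects it correctly. It misleads only someone who reads healing as healing of that component only.
- A reader might infer that the single-component information is lost. For binary outcomes the only-groups can largely be recovered by subtracting the combined group from each component group, provided the association tables show counts and both components are observed. What is missing is the specified test.
- A reader might infer that the planned aim is to show whether combined healing predicts better than either component. The protocol speaks only of association and names no reference group.
- The sizes rest on assumed cell shares, and on the extreme case where a single component has no effect at all. SAP section 5.5 does not say whether arms are pooled for this analysis, and the chance of significance is much lower per arm in Illustration 1.

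**Conclusion.** The mismatch between the documents and the overlap between the SAP groups are established from the text. Followed as written, the SAP does not examine the protocol's *alone* groups on their natural reading, and Appendix 2 does not record the change from improvement alone to healing.

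The direction of the effect needs only that doubly healed participants do better at M-44. Its size is uncertain: 9 to 16 points in Illustration 1, with a chance of significance that depends heavily on the cell shares, the rates and whether arms are pooled.

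The consequence is confined to one exploratory analysis with nominal p-values. It would be wrong to infer that any confirmatory comparison, estimand, power statement or type I error claim is affected, because M-0 healing status is used here only as a predictor of later outcome. The change is worth making because it is cheap and lets the analysis answer the question as the protocol words it.

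**What to change.** In SAP section 5.5, derive one four-level M-0 variable from the section 5.4.1.1 definitions: both, histologic healing only, endoscopic healing only, neither. Report each only-level against neither and against both, stratified by randomized treatment group, which also settles how arms are handled. If the marginal associations are kept as well, label them as marginal. Record in Appendix 2 the move from improvement alone to healing.

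The cost is one derived variable and some wording, with no new data collection. The only-groups are smaller, so their intervals will be wider. With the first mix in Illustration 1 they would number about 0.15 × 484 = 73 (histologic only) and 0.10 × 484 = 48 (endoscopic only) across all arms, against 194 and 169 in the SAP's overlapping groups.

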9.4.2. Efficacy Analyses

Unless otherwise specified, the endoscopy subscore as obtained during the central review of the video endoscopy will be used for all efficacy analyses involving endoscopy in this section.

9.4.2.1. Induction Study 1 (Phase 2b Induction Dose-ranging Study)

9.4.2.1.1. Population for Efficacy Analysis

Unless otherwise noted, efficacy analyses will be based on the **Full Analysis Set**, which is defined as all randomized participants with a modified Mayo score of 5 to 9 who receive at least 1 dose of study intervention. Participants will be analyzed according to the intervention group to which they were randomized regardless of the intervention they actually received.

9.4.2.1.2. Primary Endpoint Analysis

The primary endpoint is clinical response at Week I-12 defined as a decrease from baseline in the modified Mayo score by $\geq 30\%$ and ≥ 2 points, with either a ≥ 1 decrease from baseline in the rectal bleeding subscore or a rectal bleeding subscore of 0 or 1. The analyses will be based on the Full Analysis Set.

Participants who have a colectomy or ostomy, have protocol-prohibited medication changes (to be defined in the SAP), or who discontinued study intervention due to unsatisfactory therapeutic effect or an AE of worsening UC before the Week I-12 visit will be considered as treatment failures and considered not to be in clinical response, regardless of the actual modified Mayo score. For participants who discontinued study intervention due to COVID-19 related reasons (excluding COVID-19 infection), data at all visits after discontinuation will not be used in analysis. For participants who discontinued study intervention due to COVID-19 infection or for reasons other than lack of efficacy or an AE of worsening of UC or any other COVID-19 related reasons, their observed clinical response status (if available) at Week I-12 will be used. Participants who are missing any or all of the 3 Mayo subscores that compose the modified Mayo score or who do not return for evaluation at Week I-12 will be considered not to be in clinical response.

A precise description of the treatment effect to be estimated from the study will be described in the estimand framework. The primary estimand will use a hybrid strategy for the intercurrent events. Details on the primary estimand and other estimand definitions will be described in the SAP.

For testing of the primary endpoint, the efficacy of each guselkumab group versus placebo will be compared. For all statistical comparisons of the primary endpoint, a Cochran-Mantel-Haenszel

(CMH) test (2-sided) stratified by ADT-Failure status (Yes/No) and concomitant use of corticosteroids at baseline (Yes/No) will be used. A step-up multiple testing procedure (Hochberg 1988) will be used to control the Type-I error at a 2-sided 0.05 significance level over the comparisons for the primary endpoint. For this procedure, if p-values for both guselkumab treatment groups are ≤ 0.05 , then it will be concluded that both guselkumab treatment groups are effective compared with placebo. Otherwise, the smaller of the 2 p-values will be compared with $\alpha = 0.025$; if that p-value is ≤ 0.025 , then it will be concluded that the guselkumab treatment group associated with the smaller p-value is effective compared with placebo. The study will be considered positive if at least 1 guselkumab group is significantly different from the placebo group for the primary endpoint.

To examine the robustness of the primary endpoint analysis, sensitivity analyses of the primary endpoint will be conducted using different missing data approaches; these analyses will be described in the SAP.

Subgroup analyses of the primary endpoint will be performed based on demographic and baseline disease characteristics, baseline use and history of use of UC medications (including ADT-Failure status), and molecular predictive signature status at baseline.

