9.4.2.1.3. Major Secondary Endpoint Analyses

The major secondary endpoints are:

- Clinical remission at Week I-12.
- Symptomatic remission at Week I-12.
- Endoscopic healing at Week I-12.
- Histologic-endoscopic mucosal healing at Week I-12.
- Endoscopic normalization at Week I-12.

The same treatment failure rules that were specified for the primary endpoint analysis will also be used for the major secondary endpoints (Section 9.4.2.1.2). Participants who are missing any or all of the 3 Mayo subscores that compose the modified Mayo score or who do not return for evaluation at Week I-12 will be considered not to have achieved clinical remission. Participants who are missing both stool frequency and rectal bleeding subscores at Week I-12 will be considered not to have achieved symptomatic remission at Week I-12. Participants who have missing endoscopy subscore at Week I-12 will be considered not to have achieved endoscopic healing, endoscopic normalization, or histologic-endoscopic mucosal healing at Week I-12.

For testing of the major secondary endpoints, the efficacy of each guselkumab group versus placebo will be compared. For all statistical comparisons of the major secondary endpoints, a CMH test (2-sided) stratified by ADT-Failure status (Yes/No) and concomitant use of corticosteroids at baseline (Yes/No) will be used.

The study is not being powered to detect treatment differences between guselkumab and placebo for these major secondary endpoints. These endpoints will not be multiplicity-controlled for analysis purposes, and all p-values will be considered nominal.

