9.4.2.2.2. Primary Endpoint Analysis

The primary endpoint is clinical remission at Week I-12, defined as a stool frequency subscore of 0 or 1, a rectal bleeding subscore of 0, and an endoscopy subscore of 0 or 1 with no friability present on the endoscopy, where the stool frequency subscore has not increased from induction baseline. The analyses will be based on the Full Analysis Set.

Participants who have a colectomy or ostomy, have protocol-prohibited medication changes (to be defined in the SAP), or who discontinued study intervention due to reasons other than COVID-19 related reasons or a regional crisis, including unsatisfactory therapeutic effect or an AE of worsening UC, before the Week I-12 visit will be considered as treatment failures and considered not to be in clinical remission, regardless of the actual modified Mayo score. For participants who discontinued study intervention due to COVID-19 related reasons (excluding COVID-19 infection) or regional crisis, their observed clinical remission status at Week I-12 will be used if available. After accounting for the treatment failure rules, participants who are missing any or all of the 3 Mayo subscores that compose the modified Mayo score or who do not return for evaluation at Week I-12 will be considered not to be in clinical remission.

A precise description of the treatment effect to be estimated from the study will be described in the estimand framework. The primary estimand will use a hybrid strategy for the intercurrent events. Details on the primary estimand and other estimand definitions will be described in the SAP.

For testing of the primary endpoint, the efficacy of the guselkumab group versus placebo will be compared. A CMH test (2-sided) stratified by ADT-Failure status (Yes/No) and concomitant use of corticosteroids at baseline (Yes/No) will be used. The comparison between guselkumab and placebo will be controlled at the 2-sided 0.05 significance level. The study will be considered positive if the guselkumab group is significantly different from the placebo group for the primary endpoint.

To examine the robustness of the primary endpoint analysis, sensitivity analyses of the primary endpoint will be conducted using different missing data approaches; these analyses will be described in the SAP.

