9.4.2.3.2. Primary Endpoint Analysis

The primary endpoint is clinical remission at Week M-44, defined as a stool frequency subscore of 0 or 1, a rectal bleeding subscore of 0, and an endoscopy subscore of 0 or 1 with no friability present on the endoscopy, where the stool frequency subscore has not increased from induction baseline. The analyses will be based on the Randomized Full Analysis Set.

Participants who have a colectomy or ostomy, have protocol-prohibited medication changes (to be defined in the SAP), have a dose adjustment, or who have discontinued study intervention due to any reasons other than COVID-19 related reasons or a regional crisis, including unsatisfactory therapeutic effect or an AE of worsening UC before the Week M-44 visit will be considered not to be in clinical remission at Week M-44. For participants who discontinued study intervention due to COVID-19 related reasons (excluding COVID-19 infection) or regional crisis, their observed clinical remission status at Week M-44 will be used if available. After accounting for the treatment failure rules, participants who are missing any or all of the 3 Mayo subscores that compose the modified Mayo score or who do not return for evaluation at Week M-44 will be considered not to be in clinical remission.

A precise description of the treatment effect to be estimated from the study will be described in the estimand framework. The primary estimand will use a hybrid strategy for the intercurrent events. Details on the primary estimand and other estimand definitions will be described in the SAP.

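### Induction Study 1: discarding data after a COVID-19 logistics stop and then applying non-responder imputation can, read literally, score a measured Week I-12 responder as a failure

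*Protocol*

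**What the plan says.** Protocol Section 9.4.2.1.2 gives Induction Study 1 several rules for the primary endpoint, clinical response at Week I-12.

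- **Treatment failures.** Colectomy or ostomy, prohibited medication changes, and stops for unsatisfactory effect or an adverse event of worsening UC count as non-response.
- **COVID-19 stops other than infection.** For these, "data at all visits after discontinuation will not be used in analysis".
- **Stops for COVID-19 infection, or for reasons unrelated to efficacy, worsening UC or other COVID-19 causes.** The observed Week I-12 status is used if there is one.
- **Missing data.** The rule covers anyone lacking even one component subscore, and it ends: "or who do not return for evaluation at Week I-12 will be considered not to be in clinical response". No exception is stated.

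The other two studies treat the COVID-19 logistics stop differently. In Induction Study 2 (Section 9.4.2.2.2), "their observed clinical remission status at Week I-12 will be used if available". In the Maintenance Study (Section 9.4.2.3.2), "their observed clinical remission status at Week M-44 will be used if available". SAP Section 5.3.2 names this treatment policy (intercurrent event 5).

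For the Induction Study 1 major secondary endpoints, Section 9.4.2.1.3 says: "The same treatment failure rules that were specified for the primary endpoint analysis will also be used for the major secondary endpoints".

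**The concern.** The two Induction Study 1 sentences do not work together. Setting aside data collected after an event suits a hypothetical strategy, which asks what would have happened had the event not occurred and needs an imputation model to answer it. Scoring the participant as a non-responder is a composite strategy, which treats the event itself as a bad outcome. Doing the first and then the second discards a measured response and replaces it with failure. Neither strategy intends that.

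The result is also out of order within the section. Someone who stops because of COVID-19 infection keeps the observed outcome. Someone who stops because the site closed, an event with less connection to the drug, does not.

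At stake is the primary endpoint of Induction Study 1. Failures unrelated to treatment would lower response in every arm and shrink the difference if balanced. If unbalanced, they would bias it.

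**Working it through.** **Inputs from the plan.** Section 9.2.1 assumes response of 30% on placebo and 60% on each guselkumab dose, with a 2-sided chi-square test at 0.05. It states at least 80% power with 50 per arm (interim) and more than 90% with 130 per arm. Allocation is 1:1:1 (Section 6.3).

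**Input that is assumed.** The plan gives no rate of COVID-19 logistics stops. Let c be the share of an arm that stops for this reason and still has a Week I-12 evaluation, with the same response rate as everyone else. I take c from 0 to 10%.

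**Step 1: reproduce the plan's power.** With equal arms of size n, mean rate p̄ and difference Δ,

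power = Φ{[Δ − 1.96·√(2p̄(1 − p̄)/n)] / √([p_T(1 − p_T) + p_C(1 − p_C)]/n)}.

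- n = 50: (0.300 − 0.1950)/0.0949 = 1.107, power 86.6% (stated at least 80%).
- n = 130: (0.300 − 0.1209)/0.0588 = 3.04, power 99.9% (stated above 90%).

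Both stated figures hold.

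**Step 2: apply the literal rule.** Turning a share c into failures gives rates 0.60(1 − c) and 0.30(1 − c), so the difference is 30(1 − c) points. The Hochberg columns are simulated power per dose for the step-up rule in Section 9.4.2.1.2.

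| c, every arm | Difference (points) | n = 50, unadjusted | n = 50, Hochberg | n = 130, unadjusted | n = 130, Hochberg |
|---|---|---|---|---|---|
| 0 | 30.0 | 86.6% | about 85.5% | 99.9% | 99.9% |
| 2% | 29.4 | 85.3% | about 84% | 99.8% | 99.8% |
| 5% | 28.5 | 83.2% | about 81.5% | 99.8% | 99.7% |
| 10% | 27.0 | 79.4% | about 77% | 99.5% | 99.4% |

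With 50 per arm, power crosses 80% at c of about 9% unadjusted and about 7% under Hochberg.

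**Step 3: count participants.** At c = 5% and 130 per arm, 130 × 0.60 × 0.05 = 3.9 measured responders per guselkumab arm and 130 × 0.30 × 0.05 = 1.95 on placebo become failures.

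**Step 4: allow imbalance.** With shares c_T and c_P, the difference is 30 − 60c_T + 30c_P points. If 5% occurs in guselkumab arms only, it is 27.0 points (unadjusted power 78.6% with 50 per arm, 99.4% with 130). If 5% occurs in placebo only, it is 31.5 points, which favours the drug.

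**The case against.** **The step from discarded to failed is a reading.** Section 9.4.2.1.2 never says that discarded values become non-response. It calls the primary estimand a hybrid, leaves estimand details to the SAP, and promises sensitivity analyses with other missing-data approaches. The SAP supplied covers Maintenance only, and its introduction says that the induction studies have their own. The sentence may express a hypothetical strategy whose imputation is set out elsewhere. This stands as a limit on certainty. It does not clear the protocol text, whose only missing-data rule is non-response without exception.

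**Few participants may be affected.** Under Table 1 of the Schedule of Activities, stopping study intervention triggers an early termination visit at that time. Someone kept away by a closure or travel ban is an unlikely source of a Week I-12 endoscopy, and without one both rules give non-response. This stands, and it makes c of 5% to 10% look high. Such cases can still exist, because Section 7.1 does not withdraw participants automatically and the plan itself provides for observed status after stopping.

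**The 50-per-arm figures are illustrative.** They concern the interim, which has its own plan (Section 9.5) and selects a dose on the totality of data (Section 4.3.1). This stands.

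**Separate studies may use different rules.** True, and they have different primary endpoints. A reader might infer that aligning this one event would give the studies a common estimand. It would not. After other non-efficacy stops, Induction Study 1 uses observed status while the other two count failure, and Induction Study 1 has no regional-crisis rule.

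**Conclusion.** The point holds as a defect in the protocol text: followed literally, Section 9.4.2.1.2 scores a measured responder as a failure for a reason unrelated to the drug, unlike the handling of the same event in the other two studies. Whether the analysis does so depends on an SAP that is not supplied.

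The size is probably small. It rests on an assumed share and on affected participants responding like the rest. A balanced share shrinks the difference in proportion, which is conservative, and leaves power above 99% at 130 per arm. Imbalance could move the estimate either way, but nothing in the documents shows any, and blinding makes a systematic one unlikely.

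Two stronger readings are not supported. One is that the study's power or conclusion is in danger: the stated 80% is lost only with 50 per arm and an affected share of roughly 7% to 9% or more if balanced, or about 5% confined to the guselkumab arms. The other is that the major secondary endpoints are certainly affected: Section 9.4.2.1.3 carries over treatment failure rules, and the discard sentence does not carry that label.

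**What to change.** In Section 9.4.2.1.2 and the Induction Study 1 SAP, for COVID-19 related stops other than infection, use the observed Week I-12 clinical response status if available. Apply non-responder imputation only to what is truly missing. Keep the discard rule as a sensitivity analysis, with its imputation stated. In Section 9.4.2.1.3, say whether the same handling applies to the major secondary endpoints.

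Timing decides how this is done. Section 4.1 says that Induction Study 1 enrolment was complete before Protocol Amendment 2, and Section 6.3 releases its treatment assignments to selected sponsor personnel at its final database lock. If the study is still blinded, the primary rule can be changed. If it has been unblinded, keep the pre-specified rule and add the observed-status analysis as a labelled supplementary analysis.

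The cost is wording and one additional run of existing programs. No new data collection is needed, since only evaluations that already exist would be used. The downside is that some data from after the stop enter the analysis, as the other two studies already accept. Differences between studies on other non-efficacy stops and regional-crisis stops would remain.
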